4.6 Safety Analyses

All safety analyses will be performed on the SAF population. Missing values of safety data will not be imputed, and safety summaries will be based on the observed cases.

4.6.1 Adverse Events

A TEAE is defined as an AE that started after the first dose of study drug until 30 days after the last dose of study drug or until the last follow-up visit required by the protocol, whichever comes later.

All AEs will be coded using MedDRA terms. The number and percentage of participants with TEAEs will be tabulated for each treatment group and in total by system organ class (SOC) and preferred term (PT). The number and percentage of the participants who experienced at least one TEAE will be included. Participants will only be counted once for each preferred term. In case that a participant experienced the same event more than once, the worst severity will be presented.

An overview of TEAEs will be provided. A second overview of TEAEs will be provided which displays the overall summary of TEAEs by the categories 'Study Eye', 'Non-Study Eye', and 'Non-Ocular'.

Tabular summaries of the following AEs will be provided by SOC and PT:

- All TEAEs regardless of the relationship to study drug
- All TEAEs regardless of the relationship to study drug with frequency of $\geq 5\%$ in any treatment group
- TEAEs related to injection procedure
- TEAEs related to study drug
- TEAEs by the maximum severity grade
- TEAEs related to injection procedure by the maximum severity grade
- TEAEs related to study drug by the maximum severity grade

- All ocular TEAEs for study (see Appendix B for the definition of ocular AEs)
- Ocular TEAEs related to injection procedure for study eye
- Ocular TEAEs related to study drug for study eye
- Ocular TEAEs by the maximum severity grade for study eye
- Ocular TEAEs related to injection procedure by the maximum severity grade for study eye
- Ocular TEAEs related to study drug by the maximum severity grade for study eye
- TEAEs leading to study drug discontinuation
- TEAEs leading to study drug discontinuation related to injection procedure
- TEAEs leading to study drug discontinuation related to study drug
- Ocular TEAEs leading to study drug discontinuation for study eye
- Ocular TEAEs leading to study drug discontinuation related to injection procedure for study eye
- Ocular TEAEs leading to study drug discontinuation related to study drug for study eye
- TEAEs with high level term of cataract conditions for phakic participants for study eye
- TEAEs with high level term of cataract conditions for phakic participants for fellow eye
- All treatment-emergent serious AEs (SAEs)
- Treatment-emergent SAEs related to injection procedure
- Treatment-emergent SAEs related to study treatment
- All ocular treatment-emergent SAEs for study eye
- Ocular treatment-emergent SAEs related to injection procedure for study eye
- Ocular treatment-emergent SAEs related to study treatment for study eye
- All ocular treatment-emergent SAEs for fellow eye
- Ocular treatment-emergent SAEs related to injection procedure for fellow eye

All AEs, including non-TEAEs, will be included in individual participant listings.

The listings will include the participant identifier, age, sex, verbatim term, SOC/PT, eye (NA/OD/OS/OU), serious (yes/no), date of onset, relative study day of onset, onset before injection, after first injection or after second injection, duration of the event (or continuing), severity (mild/moderate/severe), causality (relationship to study drug/injection procedure), action taken (study drug permanently discontinued: yes/no), treatment (yes/no), and outcome (resolved/not resolved/fatal).

The same listings will be provided separately for SAEs, AEs leading to permanent discontinuation of the study treatment, AEs leading to death and deaths.

4.6.2 Clinical Laboratory Evaluation & Liver Safety Assessment

The baseline value will be the last non-missing value taken prior to the first dose of study drug.

Quantitative values evaluated by the central laboratory including hematology, biochemistry, and urinalysis will be summarized using mean, SD, minimum, maximum and median by treatment group at each analysis visit. Additionally, a within-participant change will be calculated as the post-baseline measurement minus the baseline measurement and summarized in the same way.

The incidence of participants with “Notable Laboratory Values” after the first dose of study drug will be evaluated using the criteria for Notable Laboratory Values given below. Only data collected after the first dose of study drug, up to the laboratory data taken at the Month 18 visit or 30 days after last dose of study drug will be included.

Participant listings of all notable laboratory values will also be provided; for each participant who has an analyte with a notable value, all values of that analyte taken during the study will be presented in the listing, and the notable value, and any values outside of normal limits, will be identified.

For this “Notable Laboratory Values” analysis, all laboratory values after randomization will be taken in account, i.e., any values obtained after randomization, at unscheduled visits, as well as values from the regularly scheduled laboratory visit at Month 18. Three Notable Laboratory Values participant listings will be presented: (1) notable abnormalities for participants with normal Baseline results, (2) notable abnormalities for participants with abnormal Baseline results and (3) notable abnormalities without regard to Baseline abnormalities (i.e., normal, or abnormal Baseline results). The listing without regard to Baseline abnormalities will be a composite of the previous two listings (normal Baseline, abnormal Baseline).

Laboratory analytes and primary criteria used for Notable Laboratory Values:

a. HEMATOLOGY

- i. Hemoglobin < 0.75x Baseline
- ii. Platelets < 75 or > 750 ($10^9/L$)
- iii. WBC count < 2.5 or > 17.5 ($10^9/L$)
- iv. Neutrophils (absolute) < 0.5xLLN or > 1.5xULN
- v. Eosinophile (absolute) >1.5xULN
- vi. Lymphocytes (absolute) < 0.5xLLN or >1.5xULN

b. LIVER FUNCTION

- i. Total bilirubin > 1.5xULN
- ii. Alkaline phosphatase > 1.5xULN
- iii. ASAT (SGOT) > 3xULN
- iv. ALAT (SGPT) > 3xULN
- v. GGT > 3xULN

c. RENAL FUNCTION

- i. UN > 1.3xULN
 - ii. Creatinine > 1.3xULN
- d. ELECTROLYTES
- i. Potassium < 0.9xLLN or > 1.1xULN
 - ii. Sodium < 0.9xLLN or > 1.1xULN
 - iii. Chloride < 0.9xLLN or > 1.1xULN
 - iv. Bicarbonate < 0.9xLLN or > 1.1xULN
 - v. Calcium < 0.9xLLN or > 1.1xULN
 - vi. Phosphate < 0.9xLLN or > 1.1xULN

Notable abnormalities for participants with abnormal baseline results are subject to the primary criteria above and the following secondary criteria:

- a. HEMATOLOGY
- i. Hemoglobin < 0.75x Baseline (same as primary criterion)
 - ii. Platelets < 0.75x Baseline or > 1.25x Baseline
 - iii. WBC count < 0.75x Baseline or > 1.25x Baseline
 - iv. Neutrophils (absolute) < 0.5x Baseline or > 1.5x Baseline
 - v. Eosinophils (absolute) > 1.5x Baseline
 - vi. Lymphocytes (absolute) < 0.5x Baseline or > 1.5x Baseline
- b. LIVER FUNCTION
- i. Total bilirubin > 1.5x Baseline
 - ii. Alkaline phosphatase > 1.5x Baseline
 - iii. ASAT (SGOT) > 1.5x Baseline
 - iv. ALAT (SGPT) > 1.5x Baseline
 - v. GGT > 1.5x Baseline
- c. RENAL FUNCTION
- i. UN > 1.3x Baseline
 - ii. Creatinine > 1.3x Baseline
- d. ELECTROLYTES
- i. Potassium < 0.9x Baseline or > 1.1x Baseline
 - ii. Sodium < 0.9x Baseline or > 1.1x Baseline
 - iii. Chloride < 0.9x Baseline or > 1.1x Baseline
 - iv. Bicarbonate < 0.9x Baseline or > 1.1x Baseline
 - v. Calcium < 0.9x Baseline or > 1.1x Baseline

- vi. Phosphate < 0.9x Baseline or > 1.1x Baseline

4.6.3 Vital Signs

The baseline value will be the last non-missing value taken prior to first dose of study drug. This will typically be at Screening. Any participant without a Screening value for any, or all, vital sign parameters will be considered to have a missing baseline value.

Vital sign parameters will be summarized using mean, SD, minimum, maximum and median by treatment group at each analysis visit. Additionally, a within-participant change will be calculated per visit as the post-baseline measurement minus the baseline measurement and summarized by treatment group and visit. These visits will be Month 6, Month 12, and Month 18.

4.6.4 Electrocardiograms

Number and percent of participants with normal, not clinically significant abnormal, and clinically significant abnormal results as assessed by the investigator for the 12-lead ECG will be tabulated by treatment group at each analysis visit.

A by-participant listing will be provided for ECGs which are deemed abnormal.

4.6.5 Other Safety-Related Assessments

4.6.5.1 Ophthalmic Variables

4.6.5.1.1 Ophthalmic Examination

The following ophthalmic examination variables will be analysed by treatment group using shift table from Baseline (pre-injection examination) to Month 18 or last visit available (pre-injection examination) whichever comes later (normal/abnormal, unless otherwise specified below):

- Examination of the motility
- Inspection of the lids/lacrimal/lashes
- Examination of the conjunctiva/sclera
- Inspection of the cornea
- Examination of the iris
- Examination of the pupils
- Inspection of the lens status (aphakic, pseudo-phakic, phakic; if phakic, nuclear/PSC/cortical 0, 1, 2, 3, 4), including a listing of participants with a change in lens status for study eye and (separately) for fellow eye
- Examination of the posterior vitreous detachment
- Inspection of the optic nerve
- Inspection of the macula
- Examination of the retinal vessels
- Examination of the anterior chamber activity: Cells (0, trace, 1+, 2+, 3+, 4+)
- Inspection of the vitreous haze (0, 1+, 2+, 3+, 4+)
- Examination of the vitreous haemorrhage
- Examination of peripheral retina

The following ophthalmic examination variables will be analysed by treatment group using shift table from pre-injection assessment to post-injection assessment at each monthly injection visit.

- Examination of the anterior chamber activity: Cells (0, trace, 1+, 2+, 3+, 4+)
- Inspection of the vitreous haze (0, 1+, 2+, 3+, 4+)
- Examination of the vitreous haemorrhage
- Examination of peripheral retina

4.6.5.1.2 Intraocular Pressure

IOP will be summarized by treatment group and visit, including all pre-injection, “IOP after first injection”, and “IOP after second injection” measurements for applicable visits. An additional tabular summary of the percentage of participants in categories of IOP will be presented by treatment group, visit, and injection time (pre-injection, IOP after first injection, IOP after second injection). Baseline IOP for the study eye will be taken as the average of the last two pre-treatment values, this will typically be the Screening and Day 1(D0) pre--injection values. If there is only one pre-treatment value present, then this will be the baseline value. Baseline IOP for the fellow eye will be the last pre-treatment value, this will typically be the value at Screening.

“IOP after injection” is defined as the IOP measurement that is closest in time to the protocol-specified post-injection timepoint (but at least 30 minutes post-injection). If there are two closest measurements equidistant to this timepoint, then the measurement after the protocol-specified timepoint will be used.

Mean IOP over time of all scheduled measurements (pre-injection, IOP after first injection, and IOP after second injection, etc.) will be plotted by treatment group.

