### 7.2 Tonometry

Tonometry will be performed at all timepoints specified Section 10.2 “Trial Assessments”. On days when two injections are given, the second injection may not be administered until the IOP is  $\leq 21$  mmHg or within 5 mmHg of the pre-injection IOP, at which time the IOP is recorded. After the second injection and also on days with only one injection, tonometry must be performed at least 30 minutes after the injection and IOP must return to  $< 30$  mmHg before the subject leaves the clinic. For the post-injection tonometry, proper care should be taken to minimize the risk of contamination.

Goldmann applanation tonometry must be performed at Screening, Pre-Injection (Day 1, Month 6, Month 9, Month 18) and Early Withdrawal. Tono-Pen tonometry may be used at all other timepoints, but Goldmann applanation tonometry must be used to verify IOP for a post-injection reading of  $\geq 30$  mmHg occurring more than 30 minutes post-injection, or for a reading of  $\geq 30$  mmHg at any other time.

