#### **After All Injections (including Sham injections)**

- 1) One to two minutes following each intravitreal injection, subjects should be examined by ophthalmoscopy to verify reperfusion of the central retinal artery in the immediate post-injection period. Verify that the retina is attached and that there is no new intraocular hemorrhage.
- 2) After each intravitreal injection (including Sham), check the intraocular pressure (IOP) while maintaining a clean field.
  - a. If a second injection is to be administered, monitor the IOP after the 1st injection until it is **≤ 21 mm Hg or within 5 mm Hg of the baseline IOP on the day of injection**; record the IOP at this time.

- b. The IOP should be measured and recorded 30 minutes after the last injection (whether it is the first or second injection). Monitor the IOP until it is below 30 mmHg; the subject should not be discharged until at least 30 minutes after the 2nd injection and the IOP is below 30 mmHg or at a lower level as determined by the investigator.
  - c. If a Tono-Pen is used to check pressure, a clean Tono-Pen condom should be placed on the tip before taking each measurement. If applanation tonometry is used, the applanator tip should be swabbed with alcohol and let to dry before using it to measure IOP. Sterile fluorescein strips and single use proparacaine bottles should be used for all subjects. "Fluoracaine" or other combination fluorescein sodium and proparacaine HCl mixtures should only be used if single use presentation is available, and then only if single use bottles are available. Intraocular pressure may be lowered by pharmaceutical or surgical intervention, if required. Treatment should be initiated whenever IOP is increased to the extent that the central retinal artery remains closed and the subject has NLP for more than 1-2 minutes or as per investigator judgment. Transient graying or obscuration of vision following injection, however, is expected and should not be treated. See below for additional information concerning paracentesis.

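### The SAP's single 30-minute rule for post-injection IOP does not fit the first-injection reading at the 15 two-injection visits

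*SAP*

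**What the plan says.** SAP 4.6.5.1.2 reports IOP by arm and visit, tabulates IOP categories by "injection time (pre-injection, IOP after first injection, IOP after second injection", and plots mean IOP over time. It defines a post-injection value once, for a generic after-injection reading, as the one nearest in time to the protocol's timepoint, "but at least 30 minutes post-injection". The tie rule that follows is equally general: "If there are two closest measurements equidistant to this timepoint, then the measurement after the protocol-specified timepoint will be used". Nothing there separates the first injection from the second.

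Protocol 7.2 treats the two injections differently. For the first of two it says: "On days when two injections are given, the second injection may not be administered until the IOP is" at or below 21 mmHg or within 5 mmHg of the pre-injection value, and the IOP is recorded at that moment. The 30-minute minimum is stated separately: "After the second injection and also on days with only one injection, tonometry must be performed at least 30 minutes after the injection".

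The visit sections for Months 3 to 17 (10.2.9 to 10.2.23) repeat the threshold for the first injection without a minimum time. Appendix 17.4 does the same for active drug and for Sham. Its closing part, on steps after all injections, says to monitor after the first injection until the threshold is met and then "record the IOP at this time". It ties the 30-minute reading to the last injection of the day.

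**The concern.** At a two-injection visit the SAP definition looks for something that the protocol does not set. No clock timepoint follows the first injection, only a pressure condition, so nearest to the protocol timepoint has no clear meaning. The 30-minute floor then rules out a reading taken sooner, even though that reading is exactly what the protocol asks for.

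The after-first-injection summaries, category table and plotted means could therefore hold three kinds of entry: no value at all; values only from eyes in which 30 minutes or more passed before the recorded reading; or a reading taken after injection 2 and so reflecting both injections. IOP is a listed safety endpoint and the treatment is repeated intravitreal injection, so a reader of the report will look at these tables. If time to the threshold differs between a real injection and Sham, the loss could also differ by arm. That is inference; the documents give no timing data.

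**Working it through.** **Number of visits.** Protocol 9.2.2 gives six induction administrations, two in each of three months, and monthly maintenance at Months 3 to 17 with two injections per visit.
- Two-injection visits: 17 - 3 + 1 = 15.
- Single-injection visits: 3 x 2 = 6.
- Both agree with the 15 doses of 4 mg and 6 doses of 2 mg stated in Protocol 9.2.3.
- Share of injection visits: 15 / (15 + 6) = 15 / 21 = 71%.

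**Number of planned readings.** The protocol synopsis plans about 120 participants, 60 per group.
- Per arm: 15 x 60 = 900.
- Both arms: 2 x 900 = 1,800, before dropout and missed visits.

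**What the literal rule does.** Let t be the minutes from injection 1 to the recorded between-injection reading, and s the minutes from injection 1 to injection 2, with s at least t. The protocol's reading after injection 2 falls no earlier than s + 30 minutes after injection 1.

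| Case | Between-injection reading | Reading after injection 2, as a candidate for the after-first-injection value |
|---|---|---|
| t below 30 | Fails the floor | Passes the floor, since s + 30 exceeds 30; no sentence excludes it |
| t of 30 or more | Passes the floor | Also passes, but is further from 30 minutes, because s + 30 is at least t + 30 |

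In the second row, taking 30 minutes as the timepoint, the rule selects the between-injection reading and no harm follows. In the first row it selects either nothing or a value that would also fill the after-second-injection category.

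**Number affected.** This is the number of visits in the first row. The documents contain no data on time to the threshold or on the gap between injections, so the range is 0 to 1,800.

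**Visits not in question.** At the 6 single-injection visits the protocol itself sets the 30-minute minimum, so SAP and protocol agree. The same holds for the reading after the last injection at all 21 injection visits.

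**Whether another SAP rule settles it.** The windowing steps in SAP 4.10.1 assign assessments to visits and require a pre- or post-injection record on an injection day. They do not say which reading within a visit is the first-injection one.

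**The case against.** The strongest reply is that the floor is attached to a generic after-injection reading and qualifies a timepoint that the protocol specifies. The protocol gives the first of two injections no such timepoint, so the sentence can be read as covering only the last injection. The section also opens by promising to summarise all measurements in the three categories, and SAP version 2.0 relaxed the IOP inclusion condition so as to keep more assessments. Both suggest an intent to retain readings. This reading is fair, but it leaves the first-injection value undefined, and the same edit is needed.

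A reader might infer that valid readings will be dropped, or replaced by values taken after injection 2, and that this is the usual outcome or affects every maintenance-phase value. The documents do not support that. They give no timings, and a reading taken at 30 minutes or later before injection 2 would be kept. The SAP names the two injection times as separate categories, and data-collection labels may keep them apart, although the SAP does not say so. Replacement is permitted by the wording, not shown.

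Two further objections stand. First, the consequences are limited: no test, alpha or efficacy estimate depends on these values. IOP adverse events are captured separately (SAP 4.6.1 and Appendix 2), and listings include all scheduled and unscheduled data. Second, the correct reading is taken once the threshold has been met. It is truncated by design and will not show the peak pressure rise after the first injection either.

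**Conclusion.** The mismatch is confirmed by the wording alone. At 15 of the 21 injection visits, the only SAP definition of a post-injection IOP does not describe the first-injection reading that the protocol collects. Either the floor applies and misfits, or it does not apply and no definition exists.

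The 1,800 figure (900 per arm) is a ceiling on planned readings governed by the rule. It assumes 120 participants, full attendance and both injections given at every visit. It is not a count of lost or misfiled values, which cannot be computed from the documents. The point concerns the quality of descriptive safety output and is worth correcting on that basis. It does not threaten the trial's efficacy conclusions.

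**What to change.** Amend SAP 4.6.5.1.2 only; no clinical rule changes.
- At two-injection visits, define IOP after first injection as the last recorded reading after injection 1 and before injection 2, with no 30-minute floor. Never use a reading taken after injection 2 for this category.
- Label it in tables and plot as the reading at which the second injection was released. Add a note that it is conditioned on the threshold and does not show the peak pressure rise.
- Keep the 30-minute rule for the last or only injection of the day.

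The cost is about two sentences in the SAP, a table note and a small derivation change in the tonometry analysis dataset (ADIOP). No new data are needed.

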4.7 Other Analyses

N/A

4.8 Interim Analysis (and Early Discontinuation of the Clinical Study)

There will be no interim analysis.

4.9 Sample Size Determination

The planned size of 120 participants for this phase 2b trial was determined based on the number of participants with STGD1 that could potentially be enrolled within a reasonable period of time. Based on the actual recruitment rate during the trial, this number may be increased or decreased. As STGD1 is an orphan indication, there is no natural history data currently available regarding the SD of rate of change in the area of ellipsoid zone defect over 18 months in the STGD1 patient population that we plan to enroll in this trial.

4.10 Additional Conventions

4.10.1 Analysis Windows

Scheduled Day (Study Day) for analysis windows will be calculated as: Date of visit/assessment – first dose of study drug in this study + 1.

The assignment of visits to analysis will be consistent across all by-visit analysis datasets, and will follow the respective step-by-step algorithm:

1. All assessment visits will be windowed, per the tables below, regardless of scheduled/unscheduled status, injection date, or pre/post-injection status.
2. Baseline derivations will follow the definitions as stated in the SAP.
3. Scheduled visits, that fall into their respective analysis window, will be prioritized over unscheduled visits for assignment to analysis, if multiple visits satisfy this criterion, then next priority will be given to the visit closest to the Scheduled Day as stated per the table will be used.
4. For ADPE/ADIOP only; Assessments flagged for analysis will first have the assessment date match with an exposure date (injection day) and have at least one pre-injection or one post-injection record present. The exceptions to this rule are if the analysis visit is Month 18 or if the analysis visit is Screening.
5. For ADPE/ADIOP only; If there are no scheduled assessments for a particular visit label present then any assessments which match an exposure date (injection day) may be used if there is at least one pre-injection or one post-injection measurement. Unscheduled data which do not match an injection day will not be used for replacement.

For any analysis visit for an assessment for Study Eye, the analysis visit windowing approach will follow that for visits occurring monthly. For any analysis visit for an assessment for Fellow Eye, the analysis visit windowing approach will follow that for visits occurring at either every 3 or 6 months, for further details see the tables below.

There are particular exceptions for ADLB and ADEG. These datasets will contain assessments that are only scheduled to occur twice, at Screening and Month 18. In these cases, all visits (scheduled, unscheduled, early termination) that occur after first study drug exposure will be windowed to either an early termination visit if the study day is < 534 days or Month 18 if the study day is ≥ 534 days.

Listings will include all scheduled, unscheduled, and early withdrawal data.

The definition of visit label and visit windows in reporting are described in the table below.

For visits occurring monthly (Tonometry (SE), Ophthalmic Examination (SE), Visual Acuity (SE)):

Analysis Visit	Scheduled Day (Study Day)	Analysis Window
Day 1 (D0)	1	1-1
Day 1 (D14)	15	2-23
Month 1 (D0)	30	24-37
Month 1 (D14)	44	38-53
Month 2 (D0)	61	54-68
Month 2 (D14)	75	69-83
Month 3	91	84-107
Month 4	122	108-137
Month 5	152	138-168
Month 6	183	169-198
Month 7	213	199-229
Month 8	244	230-259
Month 9	274	260-289
Month 10	304	290-320
Month 11	335	321-350
Month 12	365	351-381
Month 13	396	382-411
Month 14	426	412-442
Month 15	457	443-472
Month 16	487	473-502
Month 17	517	503-533
Month 18	548	>=534

For visits occurring every 6 months (Vital Signs, Physical Examination):

Analysis Visit	Scheduled Day (Study Day)	Analysis Window
Month 6	183	2-274
Month 12	365	275-457
Month 18	548	>=458

For visits occurring every 9 months (SD-OCT, Microperimetry, FP, FA):

Analysis Visit	Scheduled Day (Study Day)	Analysis Window
Month 9	274	2-411
Month 18	548	>=412

For visits occurring 3/6 months (Tonometry (FE), Ophthalmic Examination (FE), Visual Acuity (FE))

Analysis Visit	Scheduled Day (Study Day)	Analysis Window
Month 6	183	2-229
Month 9	274	230-320
Month 12	365	321-457
Month 18	548	>=458

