## 7.7 Laboratory Tests

The following laboratory tests will be performed as specified in Section 10.2 “Trial Assessments”:

- Hematology: hemoglobin, platelet count, white blood cell (WBC) and differential
- Renal function: serum creatinine and blood urea nitrogen (BUN)
- Hepatic function: serum bilirubin, alkaline phosphatase, gamma-glutamyl-transferase (GGT), serum glutamic oxaloacetic transaminase (SGOT)/ aspartate aminotransferase (AST) and serum glutamic pyruvic transaminase (SGPT)/ alanine aminotransferase (ALT)
- Electrolytes: sodium, potassium, chloride, bicarbonate, calcium and phosphate
- Complete urinalysis (including specific gravity, protein, blood, etc.)
- Serum pregnancy test (if of child-bearing potential)

Additional urine or serum pregnancy testing may be performed during the course of the study at the discretion of the investigator, or in accordance with local requirements or regulations.

If the Investigator judges a laboratory value outside of the normal range as clinically significant, the Investigator will repeat the laboratory determination as judged appropriate to ensure the validity of the abnormal result. If any clinically significant abnormal results are noted, the tests are to be repeated until the results are normal, are no longer considered clinically significant by the investigator, or an explanation for the change is obtained.

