### **10.2.12 Month 6 Visit (± 7 days)**

#### **Pre-injection**

- Protocol refraction and visual acuity (4 meters) using ETDRS chart (OU)
- Ophthalmologic examination and Goldmann applanation tonometry (OU)
- Spectral Domain Optical Coherence Tomography (SD-OCT) (OU)

- Fundus Autofluorescence (FAF) (OU)
- Vital signs
- Serum pregnancy test (if applicable)

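### SAP 4.10.1 labels laboratory and ECG records after first dose and before Day 534 as early termination by study day alone, so unscheduled tests in continuing participants could enter that row

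*SAP*

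**What the plan says.** SAP 4.10.1 makes an exception to its windowing for the laboratory (ADLB) and ECG (ADEG) datasets. Its premise is: "These datasets will contain assessments that are only scheduled to occur twice, at Screening and Month 18". From that it concludes that "all visits (scheduled, unscheduled, early termination) that occur after first study drug exposure will be windowed to either an early termination visit". The alternative label is Month 18, and the choice rests on timing only: a record dated before Day 534 takes the first label, and a later one takes the second.

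The general algorithm in the same section decides which record in a window is analysed. Under rule 3, scheduled visits "will be prioritized over unscheduled visits for assignment to analysis", and remaining ties go to the visit nearest the Scheduled Day. Rules 4 and 5, which restrict the use of unscheduled data, are limited to the ophthalmic examination and tonometry datasets.

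The label then defines a reported row. SAP 4.6.2 summarizes central-laboratory values and changes from baseline "by treatment group at each analysis visit". Under SAP 4.6.4 the ECG categories "will be tabulated by treatment group at each analysis visit".

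**The concern.** The SAP names unscheduled and early-termination visits as different types and then gives both the same label before Day 534. A row titled early termination will be read as the laboratory or ECG profile of people who left the trial. As written it could also contain people who stayed, and some of them could be counted at Month 18 as well.

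The row is likely to be small, so a few such records could change its count, its mean or its percentage abnormal. If one arm had more unscheduled testing, the two arms' rows would differ in composition for a reason unrelated to withdrawal.

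**Working it through.** **1. The plan's own cut-off.** SAP 4.3.2 uses 30.4375 days per month. 17 × 30.4375 = 517.4 and 18 × 30.4375 = 547.9, which give the tabulated Days 517 and 548. The midpoint is (517 + 548)/2 = 532.5, rounded up to 533. Month 17 therefore ends at Day 533 and Month 18 starts at Day 534. The same rule reproduces all 15 upper bounds from Month 3 to Month 17 in the monthly table. The cut-off is derived consistently; the point here is what it is used for.

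**2. The rule applied to each kind of record.**

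| Record | Label under SAP 4.10.1 | Did the person terminate early? |
|---|---|---|
| Screening or other pre-dose test | Baseline, outside the rule | Not applicable |
| Early Withdrawal visit before Day 534 | Early termination | Yes |
| Unscheduled test on, say, Day 60 in a participant who completes | Early termination | No |
| Recorded Month 18 visit before Day 534 | Early termination | No |
| Any post-dose test on Day 534 or later | Month 18 | Not used by the rule |

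**3. Does another rule prevent the third row?** Rule 3 only ranks records that compete for a window. Under the protocol's Section 3 schedule, a continuing participant has no haematology, chemistry, urinalysis or ECG due between first dose and Month 18. An unscheduled record is then the only candidate, and nothing outranks it. Rules 4 and 5 do not reach ADLB or ADEG.

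**4. Ranking within the window.** The tables in SAP 4.10.1 give no Scheduled Day for early termination. If a participant has two unscheduled tests before Day 534, the nearest-to-Scheduled-Day step has nothing to measure from.

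**5. A Month 18 visit before Day 534.** Protocol Section 6 targets 30-day spacing, which puts Month 18 at Day 1 + 18 × 30 = 541. The 7-day allowance in protocol 10.2.24 takes that to 541 − 7 = 534, exactly on the boundary. A completer whose mean interval is below 533/18 = 29.6 days would have the planned Month 18 tests labelled early termination. Spacing that short is possible, because the protocol requires only 21 days between monthly doses.

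**6. Illustration of size.** The documents give neither rate, so both are assumed. Let w be the share who withdraw before Day 534, all with an exit test, and r the share of the others with at least one qualifying unscheduled test. The share of the row who did not terminate is r(1 − w) / [w + r(1 − w)].

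- w = 20%, r = 2%: 0.016/0.216 = 7%
- w = 10%, r = 5%: 0.045/0.145 = 31%
- w = 5%, r = 10%: 0.095/0.145 = 66%
- r = 0: 0%

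The range restates the assumptions. It shows only that the result depends on r, which is unknown.

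**The case against.** Much can be said for leaving the rule alone, and it rules out several stronger readings.

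- **Selection for abnormality.** Protocol 7.7 says of clinically significant abnormal results that "the tests are to be repeated until the results are normal", or are no longer significant or are explained. A reader might infer that the row is therefore weighted toward abnormal values. The documents do not support this. Routine tests fall only at Screening and Month 18/Early Withdrawal. Repeats of Screening values come before randomization (protocol 8.3.12), repeats after a Month 18 test on Day 534 or later stay in Month 18, and repeats after an exit test belong to a withdrawer. A 7.7 repeat in a continuing participant before Month 18 needs an earlier ad hoc test. Repeating until normal also leaves the direction open.
- **ECG.** The protocol has no provision for repeat or for-cause ECGs. For ECG the point rests only on the SAP's inclusion of unscheduled visits.
- **Central laboratory.** The quantitative summary is limited to central-laboratory values, so locally run tests do not enter it.
- **Pregnancy tests.** Protocol 7.7 lists the serum pregnancy test among laboratory tests, and it is due at Months 6 and 12. A reader might infer that the twice-only premise is false. The schedule carries it as a separate row, nothing places it in ADLB, and SAP 4.6.2 plans no by-visit summary of it.
- **Ranking a withdrawer's exit test.** A reader might infer that it cannot be ranked against an earlier unscheduled test. The exit visit is in the protocol's schedule, so rule 3 arguably puts it first. The SAP's own list separates early termination from scheduled visits, so this is unclear, but it is not impossible to resolve.
- **Purpose and consequence.** The SAP version history says the rule was meant to clean up the Month 18 row, and it does keep earlier unscheduled tests out of it. The notable-value analysis and the listings already include unscheduled data.

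These points limit the consequence. None changes the fact that the label depends on study day alone, or supplies a rule that keeps a continuing participant's unscheduled record out of the row.

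**Conclusion.** The point holds as a labelling error in the rule as written, and it is minor. Any unscheduled central-laboratory test or ECG after first dose and before Day 534 could place a continuing participant in the early-termination row, possibly alongside a Month 18 entry for the same person. Records of equal status in that window cannot be ranked.

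This assumes that such tests are done and that the early-termination label is shown as an analysis visit in the tables, which is the natural reading of SAP 4.10.1 with 4.6.2 and 4.6.4. The number of such tests, and therefore the size and direction of any shift, cannot be derived from the documents. Only descriptive safety tables are affected; no efficacy result or hypothesis test depends on them.

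**What to change.** In SAP 4.10.1, for ADLB and ADEG:

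- Assign early termination only to the recorded Early Withdrawal visit of participants who discontinued before Month 18.
- Keep recorded Month 18 visits as Month 18, whatever their study day.
- Label other post-dose records before Day 534 as unscheduled. Leave them out of the by-visit summaries in SAP 4.6.2 and 4.6.4, and keep them, as already planned, in the notable-value analysis and listings.

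The second clause is needed so that a slightly early Month 18 visit is not swept into the unscheduled label. With one recorded exit visit per withdrawer, the missing Scheduled Day no longer matters.

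The cost is a few lines of SAP text and a flag built from the visit name and disposition data. No new data are needed.
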